8.1.9 Electronic Vaccination Report Card (eVRC)

The eVRC was developed to be administered electronically via a hand-held device. This item was structured as recommended in the final Food and Drug Administration Patient-Reported Outcome Guidance [U.S. Food and Drug Administration 2009]. The investigator or delegate will train the participant in the use of the eVRC at Visit 1 (Day 1).

Temperatures, injection-site reactions, vaccine-specific complaints, other complaints or illnesses, and concomitant medications or vaccinations will be recorded on the eVRC as

described in Section 1.3 and Section 8.3.4. The investigator or delegate will review the data captured on the eVRC with the participant at the Telephone Contact (Day 15) and Visit 2 (Day 30).

Any differences between eVRC data and the clinical database must be clearly explained in the participant's source documentation.

For the specific AEs collected via the eVRC, the investigator will use the information provided by the participant both on the eVRC and verbally at the time of eVRC review to apply the appropriate assessment of intensity and toxicity as described in Appendix 3.

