8.3.4 Safety Assessments and Use of the eVRC

All participants will be observed for at least 30 minutes after each vaccination for any immediate reactions. If any immediate AEs are observed during this period, the time at which the event occurred within this timeframe, as well as the event itself, any concomitant medications that were administered, and resolution of the event must be recorded on the appropriate eCRF.

Participants will use the eVRC (Section 8.1.9) to document the following information:

- Oral body temperatures measured Day 1 (day of vaccination) through Day 5 postvaccination
- Solicited injection-site AEs (redness/erythema, swelling, and tenderness/pain) Day 1 through Day 5 postvaccination
- Solicited systemic AEs (muscle pain/myalgia, joint pain/arthritis, headache, and tiredness/fatigue) Day 1 through Day 14 postvaccination
- Any other injection-site or systemic AEs Day 1 through Day 14 postvaccination
- Concomitant medications and nonstudy vaccinations Day 1 to Day 14 postvaccination

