9.6.2 Statistical Methods for Safety Analyses

Safety and tolerability will be assessed by clinical review of all relevant parameters, including AEs and postvaccination temperature measurements.

Consistency of the safety profile across lots will be assessed via point estimates and 95% CIs (for select safety endpoints) within each of the V114 vaccination groups (Lot 1, Lot 2, Lot 3). Details will be provided in the sSAP. The analysis of safety will then be performed for V114 overall (combining the Lot 1, Lot 2, and Lot 3 vaccination groups) versus the Prevnar 13™ vaccination group following a tiered approach as detailed below (Table 5).

The tiers differ with respect to the analyses that will be performed. AEs (specific terms as well as system organ class [SOC] terms) are either pre-specified as “Tier 1” endpoints or will be classified as belonging to "Tier 2" or "Tier 3" based on the number of events observed.

Tier 1 Events

Safety parameters or AEs of special interest that are identified a priori constitute “Tier 1” safety endpoints that will be subject to inferential testing for statistical significance with p-values and 95% CIs to be provided for between-treatment differences in the proportion of participants with events; these analyses will be performed using the Miettinen and Nurminen (M&N) method [Miettinen, O. and Nurminen, M. 1985], an unconditional, asymptotic method. For this protocol, solicited injection-site AEs (redness/erythema, swelling, and tenderness/pain) from Day 1 through Day 5 postvaccination and solicited systemic AEs (muscle pain/myalgia, joint pain/arthralgia, headache, and tiredness/fatigue) from Day 1 through Day 14 postvaccination are considered Tier 1 events.

Tier 2 Events

Tier 2 parameters will be assessed via point estimates with 95% CIs provided for differences in the proportion of participants with events (also via the M&N method) [Miettinen, O. and Nurminen, M. 1985].

Membership in Tier 2 requires that at least 36 participants in the V114 combined group (combining Lot 1, Lot 2, and Lot 3 vaccination groups) or 4 participants in the Prevnar 13™ group exhibit the event. Because many 95% CIs for Tier 2 events may be provided without adjustment for multiplicity, the CIs should be regarded as a helpful descriptive measure to be used in review, not a formal method for assessing the statistical significance of the between-group differences in AEs.

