10.3.4 Recording AE and SAE

AE and SAE recording

- When an AE/SAE occurs, it is the responsibility of the investigator to review all documentation (eg, hospital progress notes, laboratory, and diagnostics reports) related to the event.
- The investigator will record all relevant AE/SAE information on the AE CRFs/worksheets at each examination.
- It is not acceptable for the investigator to send photocopies of the participant's medical records to the Sponsor in lieu of completion of the AE CRF page.

- There may be instances when copies of medical records for certain cases are requested by the Sponsor. In this case, all participant identifiers, with the exception of the participant number, will be blinded on the copies of the medical records before submission to the Sponsor.
- The investigator will attempt to establish a diagnosis of the event based on signs, symptoms, and/or other clinical information. In such cases, the diagnosis (not the individual signs/symptoms) will be documented as the AE/SAE.

Assessment of intensity/toxicity

- An event is defined as “serious” when it meets at least 1 of the predefined outcomes as described in the definition of an SAE, not when it is rated as severe.
- The investigator will make an assessment of intensity for each AE and SAE (and other reportable safety event) reported during the study and assign it to 1 of the following categories:
 - Mild: An event that is easily tolerated by the participant, causing minimal discomfort and not interfering with everyday activities (for pediatric studies, awareness of symptoms, but easily tolerated).
 - Moderate: An event that causes sufficient discomfort to interfere with normal everyday activities (for pediatric studies definitely acting like something is wrong).
 - Severe: An event that prevents normal everyday activities. An AE that is assessed as severe should not be confused with an SAE. Severe is a category utilized for rating the intensity of an event; and both AE and SAE can be assessed as severe (for pediatric studies, extremely distressed or unable to do usual activities).
- Injection site erythema/redness or swelling from the day of vaccination through Day 5 postvaccination will be evaluated by maximum size.

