- The investigator will make an assessment of toxicity for each AE and SAE (and other reportable event) reported during the study. A toxicity grade will be assigned to injection-site AEs, specific systemic AEs, other systemic AEs, and vital sign (temperature) AEs as shown in the following tables. The toxicity grading scales used in this study are adapted from the “FDA Guidance for Industry: Toxicity Grading Scale for Healthy Adult and Adolescent Volunteers Enrolled in Preventive Vaccine Clinical Trials, September 2007.”

• **Injection-Site AE Toxicity Grading Scale**

Injection Site Reaction to Study Vaccine/Placebo^a	Grade 1	Grade 2	Grade 3	Grade 4
Injection-site AEs occurring Days 1 through 5 following receipt of study vaccine/placebo				
Pain/Tenderness	Does not interfere with activity	Repeated use of non-narcotic pain reliever >24 hours or interferes with activity	Any use of narcotic pain reliever or prevents daily activity	ER visit or hospitalization
Erythema/Redness	Size measured as B	Size measured as C or D	Size measured as E→	Necrosis or exfoliative dermatitis or results in ER visit or hospitalization
Induration/Swelling	Size measured as B	Size measured as C or D	Size measured as E→	Necrosis or ER visit or hospitalization
Other	Does not interfere with activity	Repeated use of non-narcotic pain reliever >24 hours or interferes with activity	Any use of narcotic pain reliever or prevents daily activity	ER visit or hospitalization
Any injection-site reaction that begins ≥6 days after receipt of study vaccine/placebo				
Pain/tenderness Erythema/Redness Induration/Swelling Other	Does not interfere with activity	Repeated use of non-narcotic pain reliever >24 hours or interferes with activity	Any use of narcotic pain reliever or prevents daily activity	ER visit or hospitalization

Abbreviations: AE = adverse event; ER = emergency room; eVRC = electronic Vaccine Report Card.

^aBased upon information provided by the participant on the eVRC and verbally during VRC review. Erythema/Redness and Induration/Swelling are specific injection-site AEs with size designations of letters A through E→, based upon a graphic in the eVRC. Size A is not assigned a toxicity grade; however, injection-site AEs that measure size A should be reported as adverse experiences. If the participant has an ER visit or is hospitalized for any injection-site AE, that AE is to be assigned a toxicity grade of 4, regardless of the size measured.

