Specific Systemic AE Toxicity Grading Scale

	Mild (Grade 1)	Moderate (Grade 2)	Severe (Grade 3)	Potentially Life Threatening (Grade 4)
Headache	No interference with activity	Repeated use of non-narcotic pain reliever >24 hours or some interference with activity	Significant; any use of narcotic pain reliever or prevents daily activity	ER visit or hospitalization
Fatigue	No interference with activity	Some interference with activity	Significant; prevents daily activity	ER visit or hospitalization
Myalgia	No interference with activity	Some interference with activity	Significant; prevents daily activity	ER visit or hospitalization

Abbreviations: AE = adverse event; ER = emergency room.

Other Systemic AE Toxicity Grading Scale

	Mild (Grade 1)	Moderate (Grade 2)	Severe (Grade 3)	Potentially Life Threatening (Grade 4)^b
Systemic Illness^a Illness or clinical AE (as defined according to applicable regulations)	No interference with activity	Some interference with activity not requiring medical intervention	Prevents daily activity and required medical intervention	ER visit or hospitalization

Abbreviations: AE = adverse event; ER = emergency room; eVRC = electronic Vaccine Report Card; SAE = serious adverse event.

^a Based upon information provided by the patient on the eVRC and verbally during the eVRC review during the primary safety follow-up period. For SAEs reported beyond the primary safety follow-up period, grading will be based upon the initial report and/or follow-up of the event.

^b AEs resulting in death will be assessed as Grade 4.

Vital Sign (Temperature) Toxicity Grading Scale

	Mild (Grade 1)	Moderate (Grade 2)	Severe (Grade 3)	Potentially Life Threatening (Grade 4)
Vital Signs^a Fever (°C) ^b (°F) ^b	38.0 to 38.4 100.4 to 101.1	38.5 to 38.9 101.2 to 102.0	39.0 to 40.0 102.1 to 104.0	>40.0 >104.0

^a Participant should be at rest for all vital sign requirements.

^b Oral temperature; no recent hot or cold beverages or smoking.

Assessment of causality

- Did the Sponsor's product cause the AE?

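### Does the missing joint-pain row in the toxicity scales, and the gap in the row it falls back to, call for a change to the plan?

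*Combined protocol and SAP*

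**What the plan says.** Section 9.6.2 makes seven solicited events Tier 1. Three are injection-site events. For the rest, "solicited systemic AEs (muscle pain/myalgia, joint pain/arthralgia, headache, and tiredness/fatigue) from Day 1 through Day 14 postvaccination are considered Tier 1 events". Section 8.1.9 has the investigator use the report card and the conversation with the participant to "apply the appropriate assessment of intensity and toxicity as described in Appendix 3".

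Appendix 3, Section 10.3.4, then sets up two separate ratings.

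- **Intensity** (mild, moderate, severe) depends on the effect on activity alone. The top category is "Severe: An event that prevents normal everyday activities".
- **Toxicity** is graded 1 to 4 from a set of tables: "The investigator will make an assessment of toxicity for each AE and SAE". The injection-site table names pain, redness and swelling. The Specific Systemic table names headache, fatigue and myalgia. A further Other Systemic row takes any remaining illness or clinical event.

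In the fatigue and myalgia rows Grade 3 is "Significant; prevents daily activity". In the Other Systemic row Grade 2 is "Some interference with activity not requiring medical intervention" and Grade 3 is "Prevents daily activity and required medical intervention".

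**The concern.** Joint pain is solicited, is Tier 1, and is part of a primary safety endpoint, yet it is the only one of the seven terms without its own toxicity row. The row left for it combines two criteria, activity and medical intervention, in a way that does not cover every case. A participant whose joint pain prevents activity but who has no medical intervention fits neither Grade 2 nor Grade 3. A participant with myalgia of the same effect is Grade 3. Unsolicited systemic events graded on this row meet the same gap.

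The stakes would be real if a safety conclusion rested on toxicity grade. Sites could resolve the same presentation differently, and a table of severe joint pain by arm would depend on local habit. The row also seems to apply a stricter test of severe than the intensity scale a page or so earlier.

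**Working it through.** The documents give no figure on this point, so the check is a count followed by a search for anything that uses the result.

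**Step 1: Tier 1 terms against named rows.** The inputs are the list in Section 9.6.2 and the tables in Section 10.3.4.

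- Injection site: redness, swelling, pain. Named: 3 of 3.
- Systemic: headache, fatigue, myalgia are named; joint pain is not. Named: 3 of 4.
- Total: 3 + 3 = 6 of 7 named, 1 of 7 not named.

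**Step 2: coverage of the Other Systemic row.** Cross three activity levels with medical intervention yes or no, below Grade 4 (no emergency-room care or admission): 3 × 2 = 6 combinations.

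| Effect on activity | Medical intervention | Other Systemic row | Myalgia/fatigue row | Intensity scale |
|---|---|---|---|---|
| None | No | 1 | 1 | Mild |
| None | Yes | 1 | 1 | Mild |
| Some | No | 2 | 2 | Moderate |
| Some | Yes | no grade | 2 | Moderate |
| Prevented | No | no grade | 3 | Severe |
| Prevented | Yes | 3 | 3 | Severe |

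So 2 of 6 are ungraded on the Other Systemic row and 0 of 6 on the other two scales. In the four graded cells the row and the intensity scale agree. Reading the Grade 3 conjunction as an alternative would leave 0 ungraded, but it would put no interference with intervention in both Grade 1 and Grade 3, so it does not repair the row. The six cells are a cross-classification made for this check. How often each occurs is unknown.

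**Step 3: what uses the toxicity grade.**

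- Sections 9.4.2 and 9.6.2 with Table 5: the endpoints are proportions of participants with an event. Tier 1 p-values and confidence intervals need only whether joint pain occurred.
- Tiers 2 and 3: membership depends on prespecified categories or counts of participants with the event. The temperature endpoint uses its own cut points.
- Section 9.9.2 and Table 6: detectable differences are in incidence.
- Section 9.10: the subgroup summaries are of adverse events and solicited adverse events, with no grade named.
- Section 4.4.1: no early-termination criteria are prespecified.
- Section 6.6: no dose modification is allowed; the study gives a single dose.

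No analysis, test or decision rule stated in the documents uses toxicity grade. Whatever grade, or none, is entered in the two open cells, each result named in Section 9 is the same.

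**The case for a change.** The best case for a change is that the protocol asks for a toxicity assessment it cannot always supply, for a component of a primary safety endpoint, and that closing the gap would take only a few words. Where the authors mean an event to go ungraded they say so, as for the smallest size category of redness and swelling; the Other Systemic row has no such statement. Medical intervention is not defined either, so whether a self-taken painkiller counts is open.

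Much of this stands: the row is not exhaustive, and nothing states which scale joint pain belongs to. Three neighbouring arguments do not stand.

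- **An ungraded event is not in itself a breach.** The smallest size category shows that a reportable event may carry no grade, and that affects two Tier 1 terms that do have named rows.
- **Disagreement with the intensity scale is not an error.** Nothing requires the two ratings to match, and they part elsewhere. Any narcotic use makes headache or injection-site pain Grade 3, and fever is graded by temperature alone. A record of severe intensity with Grade 2 toxicity would need a rounding-down rule that the documents do not contain; an investigator could as well enter Grade 3.
- **The wording of the term has no bearing.** Section 8.3.4 prints "Solicited systemic AEs (muscle pain/myalgia, joint pain/arthritis, headache, and tiredness/fatigue) Day 1 through Day 14 postvaccination" where Section 9.6.2 has arthralgia. Both list the same four complaints. The difference is a clerical slip or an effect of reading the text from PDF, and it does not touch the grading.

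**Conclusion.** The gap is confirmed but no change to the plan follows, because there is no gain. It concerns 1 of 7 Tier 1 terms, plus unsolicited systemic events on the same row, and 2 of 6 presentations below Grade 4. It reaches only the recorded toxicity grade. Joint-pain incidence, the Tier 1 comparison and the intensity rating are unaffected. All arms use the same scale and safety follow-up is done by blinded staff, so there is no reason to expect bias between arms. An investigator who meets an open cell can choose a neighbouring grade by clinical judgment, and the intensity rating remains as a complete measure of severity.

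This rests on three assumptions. Joint pain goes to the Other Systemic row by elimination; the documents do not say so. The tables are complete as they read here. And the supplemental SAP, DMC charter and data-entry guidelines, which are not among the documents, add no inference based on toxicity grade. If one of them tabulates grades descriptively, the handling of the two open cells belongs in that document, and the conclusions planned in Section 9 still do not move.

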10.3.5 Reporting of AEs, SAEs, and Other Reportable Safety Events to the Sponsor

AE, SAE, and other reportable safety event reporting to Sponsor via electronic data collection tool

- The primary mechanism for reporting to the Sponsor will be the electronic data collection (EDC) tool.
 - Electronic reporting procedures can be found in the EDC data entry guidelines (or equivalent).
 - If the electronic system is unavailable for more than 24 hours, then the site will use the paper AE Reporting form.
 - Reference Section 8.4.1 for reporting time requirements.
- The site will enter the SAE data into the electronic system as soon as it becomes available.
- After the study is completed at a given site, the EDC tool will be taken off-line to prevent the entry of new data or changes to existing data.
- If a site receives a report of a new SAE from a study participant or receives updated data on a previously reported SAE after the EDC tool has been taken off-line, then the site can report this information on a paper SAE form or by telephone (see next section).
- Contacts for SAE reporting can be found in the Investigator Study File Binder (or equivalent).

SAE reporting to the Sponsor via paper CRF

- If the EDC tool is not operational, facsimile transmission or secure e-mail of the SAE paper CRF is the preferred method to transmit this information to the Sponsor.
- In rare circumstances and in the absence of facsimile equipment, notification by telephone is acceptable with a copy of the SAE data collection tool sent by overnight mail or courier service.
- Initial notification via telephone does not replace the need for the investigator to complete and sign the SAE CRF pages within the designated reporting time frames.
- Contacts and instructions for SAE reporting and paper reporting procedures can be found in the Investigator Study File Binder (or equivalent).

10.4 Appendix 4: Device Events, Adverse Device Events, and Medical Device Incidents: Definitions, Collection, and Documentation

Not applicable.

10.5 Appendix 5: Contraceptive Guidance

10.5.1 Definitions

Women of Childbearing Potential (WOCBP)

A woman is considered fertile following menarche and until becoming postmenopausal unless permanently sterile (see below):

If fertility is unclear (eg, amenorrhea in adolescents or athletes) and a menstrual cycle cannot be confirmed before first dose of study intervention, additional evaluation should be considered.

Women in the following categories are not considered WOCBP:

- Premenarchal
- Premenopausal female with 1 of the following:
 - Documented hysterectomy
 - Documented bilateral salpingectomy
 - Documented bilateral oophorectomy

For individuals with permanent infertility due to an alternate medical cause other than the above (eg, Mullerian agenesis, androgen insensitivity), investigator discretion should be applied to determining study entry.

Note: Documentation can come from the site personnel's review of the participant's medical records, medical examination, or medical history interview.

- Postmenopausal female
 - A postmenopausal state is defined as no menses for 12 months without an alternative medical cause.
 - A high follicle stimulating hormone (FSH) level in the postmenopausal range may be used to confirm a postmenopausal state in women not using hormonal contraception or hormone replacement therapy (HRT). However, in the absence of 12 months of amenorrhea, confirmation with two FSH measurements in the postmenopausal range is required.
 - Females on HRT and whose menopausal status is in doubt will be required to use one of the nonhormonal highly effective contraception methods if they wish to continue their HRT during the study. Otherwise, they must discontinue HRT to allow confirmation of postmenopausal status before study enrollment.

10.5.2 Contraception Requirements

Female Participants

Contraceptives allowed during the study include^a:

Highly Effective Contraceptive Methods That Have Low User Dependency^b Failure rate of <1% per year when used consistently and correctly.

 • Progestogen-only contraceptive implant^c • Intrauterine hormone-releasing system (IUS)^c (IUS is a progestin-releasing IUD) • Intrauterine device (IUD) • Bilateral tubal occlusion

 • Azoospermic partner (vasectomized or secondary to medical cause) This is a highly effective contraception method provided that the partner is the sole male sexual partner of the WOCBP and the absence of sperm has been confirmed. If not, an additional highly effective method of contraception should be used. A spermatogenesis cycle is approximately 90 days. Note: Documentation of azoospermia can come from the site personnel's review of the participant's medical records, medical examination, or medical history interview.

Highly Effective Contraceptive Methods That Are User Dependent^b Failure rate of <1% per year when used consistently and correctly.

 • Combined (estrogen- and progestogen-containing) hormonal contraception 
 - Oral - Intravaginal - Transdermal - Injectable

 • Progestogen-only hormonal contraception 
 - Oral - Injectable

Sexual Abstinence
 
 • Sexual abstinence is considered a highly effective method only if defined as refraining from heterosexual intercourse during the entire period of risk associated with the study intervention. The reliability of sexual abstinence needs to be evaluated in relation to the duration of the study and the preferred and usual lifestyle of the participant.

Acceptable Contraceptive Methods Failure rate of >1% per year when used consistently and correctly.

 • Progesterone-only hormonal contraception where inhibition of ovulation is not the primary mode of action • Male or female condom with or without spermicide • Cervical cap, diaphragm, or sponge with spermicide • A combination of male condom with either cervical cap, diaphragm, or sponge with spermicide (double barrier methods)^d

^a. Contraceptive use by men or women should be consistent with local regulations regarding the use of contraceptive methods for participants of clinical studies.
 
^b. Typical use failure rates are higher than perfect-use failure rates (ie, when used consistently and correctly).
 
^c. If locally required, in accordance with Clinical Trial Facilitation Group (CTFG) guidelines, acceptable contraceptive implants are limited to those which inhibit ovulation
 
^d. A combination of male condom with either cap, diaphragm, or sponge with spermicide are considered acceptable, but not highly effective, birth control methods.
 
Note: The following are not acceptable methods of contraception:
 
 - Periodic abstinence (calendar, symptothermal, post-ovulation methods), withdrawal (coitus interruptus), spermicides only, and lactational amenorrhea method (LAM). - Male and female condom should not be used together (due to risk of failure with friction).

